### Subgroup Analysis

Safety, efficacy and immunogenicity endpoints may be analyzed in select subgroups specified below as applicable:

- Baseline SARS-CoV-2 Status (Positive, Negative)
- Age (6 Months to < 2 Years, 2 Years to < 6 Years, and 6 Years to < 12 Years)
- Sex (Female, Male)
- Race
- Ethnicity

- Obesity status (Obesity is defined as BMI  $\geq 95^{\text{th}}$  percentile based on WHO growth reference data)

All analyses will be conducted using SAS Version 9.4 or higher.

## 6.2. Background Characteristics

### 6.2.1. Subject Disposition

The number and percentage of subjects in the following categories will be summarized by age and vaccination group as defined in [Section 6.1](#) based on the Full analysis for Part 1 and Randomization Set for Part 2:

- Randomization Set (Part 2)
- Full Analysis Set (Part 1 and Part 2)
- Per-Protocol (PP) Set for Efficacy (Part 1 and Part 2)
- Immunogenicity Subset (Part 1 and Part 2)
- Per-Protocol (PP) Immunogenicity Subset (Part 1 and Part 2)
- Safety Set (Part 1 and Part 2)
- Solicited Safety Set (Part 1 and Part 2)
- mITT Set (Part 1 and Part 2)
- mITT1 Set (Part 1 and Part 2)

The percentage will be based on subjects in that age and vaccination group within the Full Analysis Set for Part 1 and in that age and vaccination group within the Randomization Set (as randomized) for Part 2, except the Solicited Safety Set and Safety Set for which the percentages will be based on the age and vaccination group in the Safety Set (as treated).

The number of subjects in the following categories will be summarized based on subjects screened:

- Number of subjects screened
- Number and percentage of screen failure subjects and the reason for screen failure

The percentage of subjects who screen failed will be based on the number of subjects screened. The reason for screen failure will be based on the number of subjects who screen failed.

The number and percentage of subjects in each of the following disposition categories will be summarized by age and vaccination group based on Full Analysis Set for Part 1 and summarized by age and vaccination group based on the Randomization Set for Part 2:

- Received each dose of IP
- Prematurely discontinued before receiving the second dose of IP and the reason for discontinuation
- Completed study
- Prematurely discontinued the study and the reason for discontinuation

A subject disposition listing will be provided, including informed consent date, subjects who completed the study injection schedule, subjects who completed study, subjects who discontinued from study vaccine or who discontinued from participation in the study, with reasons for discontinuation. A separate listing will be provided for screen failure subjects with reasons for screen failure.

A subject who completed 12 months of follow up after the last injection received is considered to have completed the study.

### **6.2.2. Demographics**

Descriptive statistics will be calculated for the following continuous demographic and baseline characteristics: age (months or years), weight (kg, z-score), height (cm, z-score), and body mass index (BMI) (kg/m^2, z-score). Number and percentage of subjects will be provided for categorical variables such as gender, race, ethnicity. The summaries will be presented separately by age and vaccination group as defined in [Section 6.1](#), based on the FAS, Randomization Set (Part 2), Per-Protocol (PP) Set for Efficacy, Immunogenicity Subset, Per-Protocol (PP) Immunogenicity Subset, Safety Set, mITT Set and mITT1 Set.

Participants in Part 1 and Part 2 of the study and in different age groups who receive the same mRNA-1273 dose level may be combined. If the Safety Set differs from the Randomization Set in Part 2 (e.g., subjects randomized but not received any study injection; subjects received study vaccination other than the vaccination group they were randomized to), the analysis will also be conducted using the Randomization Set.

For screened failure subjects, age (months or years), as well as gender, race, ethnicity will be presented in a listing.

In addition, subjects with any inclusion and exclusion criteria violation will also be provided in a listing.

### **6.2.3. Medical History**

Medical history data will be coded by system organ class (SOC) and preferred term (PT) using the Medical Dictionary for Regulatory Activities (MedDRA).

The number and percentage of participants with any medical history will be summarized by SOC and PT based on Safety Set. A participant will be counted only once for multiple events within each SOC and PT. SOC will be displayed in internationally agreed order. PT will be displayed in descending order of frequency and then alphabetically within SOC.

Medical history data will be presented in a listing.

### **6.2.4. Prior and Concomitant Medications**

Prior and concomitant medications and non-study vaccination will be coded using the World Health Organization (WHO) drug dictionary (WHODD). The summary of concomitant medications will be based on the Safety Set. Categorization of prior, concomitant, and post medications is summarized in [Appendix C Table 6](#).

The number and percentage of subjects using concomitant medications and non-study vaccination during the 7-day follow-up period (i.e., on the day of injection and the 6 subsequent days) and during the 28-day follow-up period after each injection (i.e., on the day of injection and the 27 subsequent days) will be summarized by vaccination groups as defined in [Section 6.1](#) as follows:

- Any concomitant medications and non-study vaccination within 7 Days Post Injection
- Any concomitant medications and non-study vaccination within 28 Days Post Injection
- Seasonal influenza vaccine within 28 Days Post Injection
- Antipyretic or analgesic medication within 28 Days Post Injection

A summary table of non-study vaccination that continued or newly received at or after the first injection through 14 days after the last injection will be provided by PT in descending frequency in the mRNA-1273 group with all dose level combined.

A summary table of concomitant medications that continued or newly received at or after the first injection through 28 days after the last injection will be provided by PT in descending frequency of the total mRNA-1273 group.

Prior, concomitant and post medications and non-study vaccination will be presented in a listing.

Concomitant Procedures will be presented in a listing.

#### **6.2.5. Study Exposure**

Study IP administration data will be presented in a listing.

Study duration will be summarized since randomization, since the first injection, and since the second injection.

#### **6.2.6. Major Protocol Deviations**

Major protocol deviations are a subset of protocol deviations that may significantly impact the completeness, accuracy, or reliability of the study data or that may significantly affect a subject's rights, safety, or well-being. Major protocol deviations rules will be developed and finalized before database lock.

The number and percentage of the subjects with each major protocol deviation type will be provided by age and vaccination group as defined in [Section 6.1](#) based on the Full Analysis Set for Part 1 and will be provided by age and vaccination group based on the Randomization Set for Part 2.

Major protocol deviations will be presented in a listing.

#### **6.2.7. COVID-19 Impact**

A listing will be provided for COVID-19 impact.

### **6.3. Safety Analysis**

Safety and reactogenicity will be assessed by clinical review of all relevant parameters including solicited ARs (local and systemic), unsolicited AEs, SAEs, MAAEs, AESIs, AEs leading to withdrawal from study vaccine and/or study participation, and physical

examination findings. Solicited ARs and unsolicited AEs will be coded by SOC and PT according to the MedDRA. Two modified versions of The Toxicity Grading Scale for Healthy Adult and Adolescent Volunteers Enrolled in Preventative Vaccine Clinical Trials (DHHS 2007) are used in this study for solicited ARs as presented in protocol section 7.4.3's Table 8 and 9; Table 8 is the pediatric toxicity scale used for children older than 36 months, and Table 9 is the infant/toddler toxicity scale used for children 6 to 36 months of age, inclusive

All safety analyses will be based on the Safety Set, except summaries of solicited ARs which will be based on the Solicited Safety Set. All safety analyses will be provided by age and vaccination group unless otherwise specified.

### **6.3.1. Adverse Events**

A treatment-emergent AE (TEAE) is defined as any event occurring during the study not before exposure to study vaccine or any event already present that worsens after exposure to study vaccine. [Note: worsening of a pre-existing condition after vaccination will be reported as a new AE.]

Adverse events will also be evaluated by the investigator for the coexistence of MAAE which is defined as an AE that leads to an unscheduled visit to a healthcare practitioner.

Unsolicited AEs will be coded by PT and SOC using MedDRA and summarized by age and vaccination group, and stage (up to 28 days after any vaccination for Part 1 and Part 2 separately, follow-up analysis period and overall stage (throughout the study); see [Section 6.1](#) for definitions of vaccination group and stage).

All summary tables (except for the overall summary of AEs) for unsolicited AEs will be presented by SOC and PT for TEAEs with counts of subjects included. SOC will be displayed in internationally agreed order. PT will be displayed in descending order of frequency of total mRNA-1273 group with all dose level combined in Part 1 and in Part 2 correspondingly and then alphabetically within SOC. When summarizing the number and percentage of subjects with an event, subjects with multiple occurrences of the same AE or a continuing AE will be counted once. Subjects will be presented according to the highest severity (the strongest relationship) in the summaries by severity (of related AEs), if subjects reported multiple events under the same SOC and/or PT.

Percentages will be based upon the number of subjects in the Safety Set within each age and vaccination group for Part 1 and Part 2 separately.

### **6.3.1.1. Incidence of Adverse Events**

An overall summary of unsolicited TEAEs including the number and percentage of subjects who experience the following will be presented:

- Any unsolicited TEAEs
- Any serious TEAEs
- Any fatal TEAEs
- Any unsolicited medically-attended TEAEs
- Any unsolicited TEAEs leading to discontinuation from study vaccine
- Any unsolicited TEAEs leading to discontinuation from participation in the study
- Any unsolicited Grade 3/Severe TEAEs
- Any unsolicited Grade 3 or higher TEAEs
- Any unsolicited Non-serious TEAEs
- Any unsolicited Non-serious and Grade 3/Severe TEAEs
- Any unsolicited Non-serious and Grade 3 or higher TEAEs
- Any AESI of MIS-C
- Any AESI of myocarditis and/or pericarditis
- Any AESI other than MIS-C and myocarditis and/or pericarditis

The table will also include number and percentage of subjects with unsolicited TEAEs that are treatment-related in each of the above categories.

In addition, separate listings containing individual subject adverse event data for unsolicited AEs, unsolicited TEAEs leading to discontinuation from study vaccine, unsolicited TEAEs leading to discontinuation from participation in the study, serious AEs, unsolicited medically-attended AEs, AESI other than MIS-C and myocarditis and/or pericarditis, AESI of MIS-C and AESI of myocarditis and/or pericarditis will be provided separately.

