## **3. Study Endpoints**

### **3.1. Primary Endpoints**

The primary safety objective for Part 1 open-label phase or Part 2 blinded phase and open-label phase will be evaluated by the following safety endpoints:

- Solicited local and systemic adverse reactions (ARs) through 7 days after each injection
- Unsolicited adverse events (AEs) through 28 days after each injection
- Medically-attended AEs (MAAEs) through the entire study period
- Serious AEs (SAEs) through the entire study period
- AEs of special interest (AESIs), including multisystem inflammatory syndrome in children (MIS-C) and myocarditis and/or pericarditis, through the entire study period

The primary safety objective of mRNA-1273 booster or third dose will be evaluated by the following safety endpoints:

For mRNA-1273 Booster/Third Dose:

- Solicited local and systemic ARs through 7 days after booster or third dose
- Unsolicited AEs through 28 days after booster or third dose
- MAAEs through the entire study period after booster or third dose
- SAEs through the entire study period after booster or third dose
- AESIs through the entire study period after booster or third dose
- AEs leading to discontinuation from study participation after booster or third dose through the last day of study participation

For mRNA-1273.214 Booster Dose:

- MAAEs through the entire study period after booster dose
- SAEs through the entire study period after booster dose
- AESIs through the entire study period after booster dose
- AEs leading to discontinuation from study participation after booster dose through the last day of study participation

The primary immunogenicity objective for Part 1 open-label phase or Part 2 blinded phase and open-label phase will be evaluated by either:

- The proportion of participants with a serum antibody level at Day 57  $\geq$  antibody threshold of protection. If an accepted serum antibody threshold of vaccine protection against COVID-19 is available, this analysis will form the basis to infer efficacy.

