### **6.3.2. Solicited Adverse Reactions**

An AR is any AE for which there is a reasonable possibility that the test product caused the AE. The term “Solicited Adverse Reactions” refers to selected signs and symptoms occurring after injection administration during a specified post-injection follow-up period

(day of injection and 6 subsequent days). The solicited ARs are recorded by the subject in eDiary. The occurrence and intensity of selected signs and symptoms is actively solicited from the participant during a specified post-injection follow-up period (day of injection and 6 subsequent days), using a pre-defined checklist (i.e., solicited ARs).

The following local ARs will be solicited by the eDiary: pain at injection site, erythema (redness) at injection site, swelling (hardness) at injection site, localized axillary swelling or tenderness ipsilateral to the injection arm, and groin or underarm swelling or tenderness ipsilateral to the side of injection.

The following systemic ARs will be solicited by the eDiary: headache, fatigue, myalgia (muscle aches all over the body), arthralgia (aching in several joints), nausea/vomiting, fever, chills, irritability/crying, sleepiness, and loss of appetite.

The AR categories are different for younger population between Age 37 months to <12 years and Age 6 months to  $\leq$  36 months. Details presented in Table 8 and 9 in the protocol.

The solicited ARs will be graded based on the grading scales presented in Table 8 and 9 in the protocol, modified from the Toxicity Grading Scale for Healthy Adult and Adolescent Volunteers Enrolled in Preventative Vaccine Clinical Trials (DHHS 2007). Investigator will assess Grade 4 events (with exception of fever).

If a solicited local or systemic AR continues beyond 7 days post injection, the participant's parent(s)/ LAR(s) will be prompted to capture details of the solicited local or systemic AR in the eDiary until it resolves or the next IP injection occurs, whichever occurs first.

All solicited ARs (local and systemic) will be considered causally related to injection.

After booster doses with mRNA-1273.214, local or systemic ARs will only be reported on the eCRF if they are medically attended, considered serious or lead to discontinuation from the study. No eDiaries will be used after booster doses with mRNA-1273.214.

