#### **3.3. Booster (Part 1 and Part 2)/Third Dose (Part 3)**

##### **3.3.1. Primary Safety Endpoints**

For mRNA-1273 Booster/Third Dose:

- Solicited local and systemic ARs through 7 days after booster or third dose
- Unsolicited AEs through 28 days after booster or third dose
- MAAEs through the entire study period after booster or third dose
- SAEs through the entire study period after booster or third dose
- AESIs through the entire study period after booster or third dose
- AEs leading to discontinuation from study participation after booster or third dose through the last day of study participation

For mRNA-1273.214 Booster Dose:

- MAAEs through the entire study period after booster dose
- SAEs through the entire study period after booster dose
- AESIs through the entire study period after booster dose
- AEs leading to discontinuation from study participation after booster dose through the last day of study participation

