### **6.3.1.1. Incidence of Adverse Events**

An overall summary of unsolicited TEAEs including the number and percentage of subjects who experience the following will be presented:

- Any unsolicited TEAEs
- Any serious TEAEs
- Any fatal TEAEs
- Any unsolicited medically-attended TEAEs
- Any unsolicited TEAEs leading to discontinuation from study vaccine
- Any unsolicited TEAEs leading to discontinuation from participation in the study
- Any unsolicited Grade 3/Severe TEAEs
- Any unsolicited Grade 3 or higher TEAEs
- Any unsolicited Non-serious TEAEs
- Any unsolicited Non-serious and Grade 3/Severe TEAEs
- Any unsolicited Non-serious and Grade 3 or higher TEAEs
- Any AESI of MIS-C
- Any AESI of myocarditis and/or pericarditis
- Any AESI other than MIS-C and myocarditis and/or pericarditis

The table will also include number and percentage of subjects with unsolicited TEAEs that are treatment-related in each of the above categories. Safety summary tables for booster/third dose analysis will be provided separately.

In addition, listings containing individual subject adverse event data for unsolicited AEs, unsolicited TEAEs leading to discontinuation from study vaccine, unsolicited TEAEs leading to discontinuation from participation in the study, serious AEs, unsolicited medically-attended AEs, AESI other than MIS-C and myocarditis and/or pericarditis, AESI of MIS-C and AESI of myocarditis and/or pericarditis will be provided separately for placebo-mRNA-1273 group in Part 2 open-label phase and the group receiving booster/third dose in booster/third dose analysis. In Part 2, the safety data for the original

mRNA-1273 group in open-label will be included in blinded listings with a flag for open-label phase.

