2. Symptom-directed physical examination will be performed at the BD-D1. On dosing day before injection, the arm receiving the injection should be examined and the associated lymph nodes should be evaluated. At visits BD-3 (BD-D29), BD-4 (BD-D181) and BD-6 (BD-D366), a symptom-directed physical examination may be performed at the discretion of the investigator. Any clinically significant finding identified during a study visit should be reported as a MAAE. An oral or tympanic temperature should be taken on the day of injection (BD-D1) prior to dosing. Participants who are febrile (body temperature  $\geq 38.0^{\circ}\text{C}/100.4^{\circ}\text{F}$ ) before dosing (BD-D1) must be rescheduled to receive the injection. Afebrile participants with minor illnesses can be vaccinated at the discretion of the investigator.
3. Pregnancy test at BD-D1 before the booster dose injection will be a point-of-care urine test and will be performed if deemed appropriate by the investigator. At the discretion of the investigator, a pregnancy test either via blood or point-of-care urine test can be performed at any time during the study.
4. Sample should be collected prior to dosing on BD-D1.
5. Post-dosing, participants will have a 30-minute observation period. If any concerning symptoms occur, investigator may check vital signs during this period (however, no routine vital signs necessary after vaccination if no concerning symptoms).
6. An unscheduled visit may be prompted by reactogenicity issues, or new or ongoing AEs.
7. The nasal swab sample must be collected prior to injection at the BD-1 visit.
8. Trained study personnel will call all participants to collect information relating to any MAAEs (including any signs and symptoms of COVID-19), AESI, AEs leading to withdrawal, SAEs, information on concomitant medications associated with those events, and any non-study vaccinations. Any solicited AR or AE that meets any of the following criteria must be entered into the participant's eCRF:1) An Event, including local or systemic AR, that results in a visit to a healthcare practitioner (HCP) (MAAE). 2) An Event, including local or systemic AR, leading to the participant withdrawing from the study or the participant being withdrawn from the study by the Investigator (AE leading to withdrawal) 3) An Event, including local or systemic AR, that otherwise meets the definition of an SAE. 4) Any AESI.

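### Medically attended AEs and, after booster or third doses, AEs leading to study discontinuation are unrestricted primary safety endpoints, but every table and listing of them is limited to unsolicited events

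*SAP*

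**What the plan says.** The document holds two SAPs: one for Part 1 and the blinded phase of Part 2 (the primary-series SAP), and one for the Part 2 open-label phase, boosters and Part 3 (the booster SAP).

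**Endpoints.** Section 3.1 of the primary-series SAP lists "Medically-attended AEs (MAAEs) through the entire study period" for Parts 1 and 2, and "MAAEs through the entire study period after booster or third dose" for the later doses. Section 3.3.1 of the booster SAP adds "AEs leading to discontinuation from study participation after booster or third dose through the last day of study participation". The mRNA-1273.214 booster has four primary safety endpoints, and MAAEs and AEs leading to study discontinuation are two of them. None of these entries is limited to unsolicited events.

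**Definitions.** Section 6.3.1 refers to an "MAAE which is defined as an AE that leads to an unscheduled visit to a healthcare practitioner". Section 6.3.2 describes an adverse reaction (AR) as a kind of AE and adds: "All solicited ARs (local and systemic) will be considered causally related to injection".

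**Outputs.** Section 6.3.1.1 of both SAPs has the rows "Any unsolicited medically-attended TEAEs" and "Any unsolicited TEAEs leading to discontinuation from participation in the study", plus a matching row for discontinuation from study vaccine. The SOC/PT tables in 6.3.1.2 and the listings in 6.3.1.1 repeat the restriction.

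**The concern.** The endpoint sections and the output sections describe different sets of events. If the programmers follow the output sections, declared primary safety endpoints are undercounted.

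The missing events are not a random sample. They are injection reactions serious enough to the family to prompt a healthcare visit or, after a booster or third dose, withdrawal from the study. By the SAP's own rule they are all related to the injection, so the treatment-related MAAE rows and tables lose a class of events that belongs there by definition. In the blinded Part 2 comparison, the omission would favour the vaccine if such reactions are more frequent on mRNA-1273 than on placebo.

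**Working it through.** The SAP gives no figure to reproduce, so the check compares its sections and traces one event through them.

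**1. Does the event meet the endpoint?** Take a non-serious fever, not an AESI, that falls within the 7-day solicitation period and leads to an unscheduled healthcare visit.
- Section 6.3.2: it is a solicited AR, and an AR is an AE.
- Section 6.3.1: an AE that leads to an unscheduled visit is an MAAE.
- Sections 3.1 and 3.3.1: MAAEs are a primary safety endpoint, without restriction.
- Booster SAP, Appendix J, footnote 8 makes the link explicit for mRNA-1273.214: "An Event, including local or systemic AR, that results in a visit to a healthcare practitioner (HCP) (MAAE".

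The event meets the endpoint. If it led to study withdrawal after a booster or third dose, it also meets the discontinuation endpoint.

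**2. Where would it be counted?**

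| Output | Scope as written | Event included? |
|---|---|---|
| Overall summary, MAAE row (6.3.1.1, both SAPs) | unsolicited | no |
| Overall summary, discontinuation rows (6.3.1.1, both) | unsolicited | no |
| SOC/PT tables, MAAE and discontinuation (6.3.1.2, both) | unsolicited | no |
| MAAE and discontinuation listings (6.3.1.1, both) | unsolicited | no |
| Serious and AESI rows (6.3.1.1, both) | no such limit in the row | no: neither serious nor an AESI |
| Solicited AR tables (6.3.2, both) | grade, day, onset, duration | yes after mRNA-1273, but not by medical attendance or withdrawal |

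The event enters no MAAE or discontinuation count.

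**3. The mRNA-1273.214 booster.** Section 6.3.2 says that no eDiary is used and that local or systemic ARs are reported only if medically attended, serious or leading to study discontinuation. Section 6.2.1 of the booster SAP lists only the Full Analysis Set and the Safety Set for this product, with no Solicited Safety Set. Two readings follow:
- The reported ARs are not classed as unsolicited. Non-serious, non-AESI ones then enter no table.
- They are classed as unsolicited. The MAAE and discontinuation counts then include reactions after mRNA-1273.214 but not after the mRNA-1273 booster, so the same endpoint differs in scope between products.

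The SAP does not say which reading applies.

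**4. Size.** Let q be the proportion of children whose only MAAE is a solicited AR. The MAAE row is understated by q in each arm, and the risk difference by q(vaccine) − q(placebo). The SAP gives neither value. As pure assumption, suppose 0.5% to 2% of mRNA-1273 children and 0.2% to 0.5% of placebo children see a practitioner for a solicited AR. The difference then runs from 0.5 − 0.5 = 0.0 to 2.0 − 0.2 = 1.8 percentage points. Even these are proportions with any such visit. Subjects are counted once per row, so a child with another, unsolicited MAAE is already included and q is smaller. The range has no support in the SAP and shows only that the size is undetermined.

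**The case against.** The strongest defence is that the restriction is disclosed and that little is lost. Section 6.3.1.1 presents its table as a summary of unsolicited events. Solicited ARs after mRNA-1273 are tabulated in detail by grade and day, and for the primary series they are also listed. Serious reactions fall in the serious rows. Disposition tables give reasons for leaving the study. The SAP does not define an unsolicited AE, and the protocol may say that a medically attended solicited AR is also recorded as an AE.

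Much of this stands as a limit on the point. The reactions do not vanish: after mRNA-1273, what is lost is the medically attended or withdrawal status of non-serious, non-AESI ones. It does not remove the mismatch. The restricted rows are the only planned MAAE outputs and the only AE-based discontinuation outputs, and no solicited AR table or disposition table substitutes for them. Any rule in the protocol would have to be reconciled with the SAP, which states in section 1 that it prevails where methods differ.

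Three stronger readings are tempting but unsupported.
- A reader might infer that reactions after mRNA-1273.214 are counted, so that MAAE rates for the two boosters are shown not to be comparable. Section 6.3.2 and Appendix J say only that they are reported or entered on the eCRF. The table wording is the same for both products.
- A reader might infer that stopping vaccination is an endpoint. It is not listed as one. Discontinuation from study participation is an endpoint only after booster or third doses. For the primary series, AEs leading to withdrawal are a safety parameter in section 6.3.
- A reader might infer a proven bias of known size towards the vaccine. The direction depends on reaction rates that the SAP does not give, and the placebo comparison exists only in the blinded phase of Part 2. The booster and third-dose analyses are open-label.

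**Conclusion.** The point holds as an internal contradiction. MAAEs, and after booster or third doses AEs leading to study discontinuation, are declared without restriction, while every output that reports them is limited to unsolicited events. Followed as written, the plan leaves non-serious, non-AESI solicited ARs out of these counts, and the treatment-related MAAE counts are the most affected.

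The conclusion rests on the ordinary reading that a solicited AR is not also an unsolicited AE, which the SAP neither states nor contradicts. The size cannot be calculated. A bias towards the vaccine in the blinded comparison is conditional on medically attended reactions being more frequent on mRNA-1273 than on placebo. For mRNA-1273.214 the defect is an unstated classification, and either answer leaves a problem. This should be corrected, but it does not undermine the solicited AR, serious or AESI analyses.

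**What to change.** - In 6.3.1.1 and 6.3.1.2 of both SAPs, remove *unsolicited* from the MAAE and discontinuation rows, tables and listings. Alternatively, keep those rows and add parallel ones that include solicited ARs that were medically attended or led to discontinuation. Parallel rows preserve continuity with any output already produced.
- Apply the same rule to the primary series, the mRNA-1273 booster, the third dose and mRNA-1273.214.
- State whether local and systemic ARs reported after mRNA-1273.214 are classed as solicited or unsolicited, and in which tables they appear.
- In section 6.3 of the booster SAP, provide for MedDRA coding of these solicited ARs. It mentions coding only for unsolicited AEs, whereas the primary-series SAP codes both.
- Confirm that medical attendance and withdrawal are recorded against solicited ARs. Section 6.3.1 has the investigator evaluate AEs for MAAE status, which suggests that they are.

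The cost is wording, a few more rows and some coding. The reported MAAE and discontinuation rates will be slightly less favourable.
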